Protocol

The prediction of failure rate of dental implants

NCT number: Unknown yet

Document date: 21-9-2018

During the past decades, dental implant therapy has developed into a successful treatment option for patients confronted with both partial and complete edentulism. Based on the literature, the survival rate of dental implants, which is defined that the dental implants are still in the mouth after insertion, is around 95% in the 5-year follow-up and around 90% in the 10-year follow-up [1-3]. The success rate of dental implants, which is defined as dental implants in function, with good hard and soft tissue physiology and user satisfaction ranges from 85.2% to 88.7% in the follow-up of up to 20 years [4-6]. This indicates that both the success rate and survival rate of dental implants is high. However, both survival rates and success rates vary across patients with different profiles. The expense of dental implant treatment is high and implant placement is a surgical procedure which is invasive and thus risky for the patients' health. Once the failure of dental implants occurs, it may cause some severe negative consequences for patients. For example, the failure will cause a financial loss for patients and a possible shock concerning both mental and physical aspects. To reduce these risks it is important and necessary for clinicians to be able to predict the risk of the failure of dental implants of individual patients before they undergo dental implant treatment.

Aim:

The aim of the project is to identify important risk factors for failure of dental implants and to develop a prediction model for the failure rate of dental implants at follow-up as a tool for clinicians to establish patients individual risk profile.

Methods:

Study design

The study is a retrospective design. The clinical data of all the adult patients who were referred to the Department of Oral Implantology and Prosthetic Dentistry, Academic Centre for Dentistry Amsterdam (ACTA) at their first intake for placement of dental implant(s) from September 2009 to September 2013 are collected retrospectively from the clinical data management system of ACTA in the study.

Predictors

The initial list of potential predictors for the failure of implants is first determined based on previous literature and the Dutch Clinical Practice Guideline (KPR). Then, the list of the predictors is sent to the international experts from the International Team for Implantology (ITI) for further screening. Finally, the short list of the potential predictors is determined based on the experts' opinions and the availability of the predictors in the clinical data management system of ACTA. The potential predictors include five domains: patients' demographic characteristics, lifestyle habits, general health, dental health, and implant characteristics.

Outcomes

The outcomes include the follow-up time of implants and whether the failure of the implants is observed at the follow-up. The follow-up time is defined as a period in days starting from the date at the placement of suprastructure (baseline) to the date at the last follow up time or the

date when the failure is observed. The failure of implants is defined as the presence of peri-implantitis, presence of mobility of implants, or removal of the implants for any reasons, for instance, unacceptable performance in aspects of function, tissue physiology, esthetics, and patients' satisfaction after placement of suprastructure.

Statistical analysis

The univariate and multivariate Cox regression analysis is used to identify important risk factors for the failure of dental implants and to develop the model. Then, the performance of the models, in aspects of calibration and discrimination, is assessed. Calibration is defined as the agreement between predicted outcomes and observed outcomes. For assessment of calibration, the included implants are separately grouped into deciles based on their predicted risk of failure. The calibration of the model is assessed by plotting the predicted risk of failure against 1 minus the individual Kaplan-Meier estimate for each decile in the follow-up. Discrimination is defined as the ability of the model to differentiate between those with and without outcome events. The discrimination of the model in the follow-up is assessed with the concordance index (C-index). Then, the model is converted to a score chart and line chart in order to facilitate the calculation of the failure rate of implants. The score of each included predictor is produced by the regression coefficients being divided by the smallest regression coefficient among the predictors and subsequently rounded. Finally, the clinical values of the model are assessed, using prevalence, sensitivity, specificity, positive predictive value (PPV), and negative predictive value (NPV) of the model at the optimal cutoff score.

All the statistical procedures are performed with SPSS software 25.0 (IBM, New York, the USA) and R software 3.2.3 (R Development Core Team, Vienna, Austria).

What is already known:

Recently, there are many studies focusing on the evaluation of survival rate of implants based on longitudinal cohorts. However, they mainly reported the values of the failure rate of implants in the follow-up (like 5-year survival rate) or compared the failure rate of different types of implants. These types of studies are beneficial for the groups of patients but not for the individual patients. Also, there are several studies focusing on the prognostic factors that may be associated with the survival rate of dental implants. But these studies belonged to prediction factor studies instead of prediction modeling studies. The findings in these studies are difficult to directly apply to clinical practice.

However, there is a very limited number of studies focusing on the prediction of survival rate (or failure rate) of implants in the follow-ups. For example, Chuang et al. (1) used a clustered marginal approach to predict the survival rate in 2002 and found that among those who had a delayed procedure, did not smoke, and underwent a two-stage implant procedure, the predicted 1- and 5-year survival rates were 97.2% and 93.4%, respectively. For those who had an immediate implant placed, smoked, and underwent a one-stage procedure, the predicted survival rates were 58.5% and 27.6%, respectively. In 2006, Chuang and Cai (2) used Cox proportional hazards frailty model to predict the future implant survival based on some predictors including smoking status, the timing of placement of the implant and implant staging.

In this study, they predicted that for a non-smoking individual with 2 implants placed, an immediate implant and in one stage, the probability that 1 implant would survival 12 months was 85.8% and the joint probability of surviving for 12 months was 75.1%. If 1 implant was placed earlier and had survived for 12 months, then the second implant had an 87.5% chance of surviving 12 months. However, in these two studies, the authors only included a small number of predictors and did not develop a score chart for the individual patients. Also, the performance of the models was not assessed.

What is the project will add:

The project can provide clinicians with the predicted probability of the failure rate of dental implants of each individual patient preoperatively. The model may be helpful for clinicians to make decisions about the postoperative care for the patients. Also, the model can help shape the patients' expectations about the survival of dental implants.

What is new:

In the project, we will use some more predictors to predict the survival rate of dental implants to make the prediction model more accurate. Also, we will develop a score chart for clinicians. In this score chart, clinicians can easily calculate the sum score of each patient and find out the corresponding predicted probability of the failure rate of dental implants of each individual patient. The score chart is very easy-to-use in the clinical practice. Besides, in this project, the methodology (the prediction model developed with Cox regression analysis) is novel in dentistry.

References:

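### The clock starts at suprastructure placement, so implants lost earlier are never counted, yet the model is offered as a preoperative risk

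*Combined protocol and SAP*

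**What the plan says.** Under Study design, the data come from all adult patients referred to the department "at their first intake for placement of dental implant(s) from September 2009 to September 2013". That point precedes any implant.

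Under Outcomes, the time origin is later: "The follow-up time is defined as a period in days starting from the date at the placement of suprastructure (baseline". Failure is a composite: "The failure of implants is defined as the presence of peri-implantitis, presence of mobility of implants, or removal of the implants for any reasons". The examples that follow end with "tissue physiology, esthetics, and patients' satisfaction after placement of suprastructure".

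The Statistical analysis section gives the modelling method: "The univariate and multivariate Cox regression analysis is used to identify important risk factors for the failure of dental implants and to develop the model". Calibration is assessed within deciles of the included implants by "plotting the predicted risk of failure against 1 minus the individual Kaplan-Meier estimate for each decile in the follow-up".

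Two places state when the prediction is meant to be used. The introduction says clinicians need to be able to "predict the risk of the failure of dental implants of individual patients before they undergo dental implant treatment". The section on what the project will add says: "The project can provide clinicians with the predicted probability of the failure rate of dental implants of each individual patient preoperatively". That section also names decisions about postoperative care as a use.

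Nowhere is it said how implants lost before the suprastructure, or never restored, are handled. Nor is the prediction limited to restored implants.

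**The concern.** The intended prediction and the analysed time scale refer to different populations. Before surgery, the patient faces every failure from insertion onwards. The model sees only failures among implants that survived to restoration. The score chart is the main product of the project, and it would give individual patients a probability that leaves out the early phase. The omission is in the falsely reassuring direction.

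The plan's own performance checks would not reveal this. Predicted risk and Kaplan-Meier risk are both computed in the same restored implants, so calibration can look good while the preoperative risk is understated.

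**Working it through.** **1. Does the time definition exclude early losses?** The plan has no explicit exclusion, so this is an inference. Follow-up runs from suprastructure placement to failure or last follow-up. An implant removed before that date has no start date, so it has no valid follow-up time and can be neither at risk nor an event in the Cox model. The closing words of the failure definition may qualify the whole definition or only the examples. If they qualify only the examples, removal for any reason could include early removal, but such an implant would still have no follow-up time.

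**2. General size.** The plan states no event count, early-loss rate or prediction horizon, so there is no figure of its own to reproduce. Let e be the proportion lost before suprastructure and p the displayed risk after it, both to the same end date.

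- Risk from insertion = e + (1−e)p
- Gap = e + (1−e)p − p = e(1−p)

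The gap is positive whenever e > 0 and p < 1, and zero if e = 0. With assumed ranges:

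- smallest: e = 0.5%, p = 25%: 0.005 × 0.75 = 0.4 points
- largest: e = 5%, p = 5%: 0.05 × 0.95 = 4.8 points

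**3. Illustration from figures in the protocol.** The section on what is already known cites a 2002 clustered marginal analysis with predicted 1- and 5-year survival of 97.2% and 93.4% (delayed, non-smoking, two-stage) and 58.5% and 27.6% (immediate, smoking, one-stage). My assumptions are that these count from placement, that the suprastructure comes at t = 0.25–0.5 years, and that the hazard is constant within year 1.

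- S(t) = S1^t; early loss = 1 − S(t)
- Displayed risk to 5 years after placement = 1 − S5/S(t)
- Full risk = 1 − S5

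| Profile | t (years) | Early loss | Displayed | Full | Gap (points) | Relative gap |
|---|---|---|---|---|---|---|
| Low risk | 0.25 | 0.71% | 5.9% | 6.6% | 0.7 | 10% |
| Low risk | 0.5 | 1.41% | 5.3% | 6.6% | 1.3 | 20% |
| High risk | 0.25 | 12.5% | 68.4% | 72.4% | 4.0 | 5% |
| High risk | 0.5 | 23.5% | 63.9% | 72.4% | 8.5 | 12% |

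**4. Composite outcome.** Those figures are for survival, whereas the plan also counts peri-implantitis and mobility. Suppose a further q = 10–20% of restored implants fail in these ways by 5 years, independently (assumed). Displayed risk is then 1 − (S5/S(t))(1−q), against 1 − S5(1−q) in full.

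- Low risk: 15.3–14.7% against 15.9% (q = 10%); 24.7–24.2% against 25.3% (q = 20%). Gap 0.5–1.2 points (2–8% relative).
- High risk: 71.6–67.5% against 75.2%; 74.8–71.1% against 77.9%. Gap 3.2–7.6 points (4–10% relative).

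**5. Horizon of 5 years after suprastructure.** Carry the year 1–5 hazard forward, h = ln(S1/S5)/4 = 0.00997 (low) and 0.188 (high). Displayed risk, 1 − S5·exp(−ht)/S(t), is 6.17–5.74% and 69.9–67.1%. The gaps to the 5-year risk from placement (6.6% and 72.4%) fall to 0.4–0.9 and 2.5–5.3 points.

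**The case against.** The strongest objection concerns direction. The plan's clock runs from the suprastructure, its outcome is composite, and it states no horizon. Combine steps 4 and 5, with the q hazard constant and carried forward. The displayed 5-year risk for the low-risk profile becomes 16.0–16.2% against 15.9% (q = 10%), or 25.8–26.4% against 25.3% (q = 20%), which is slightly too high. For the high-risk profile it stays too low, by 1.7–4.4 points. This arithmetic is right. But it compares a window that ends 5 years after suprastructure with one that ends 5 years after placement, and the extra 3–6 months at risk offset the missing early losses. To the same end date the sign does not change. What stands is that the direction claim needs that qualification.

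It is also fair that the size rests on assumptions. The same 3–6 month interval is applied to two treatment schedules that the protocol itself distinguishes, and the 8.5-point maximum needs 23.5% early loss, far above the 0.5–5% used in the general range. Only e(1−p), with e unknown, is firm.

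Starting at the suprastructure is a legitimate choice, and the wording of the failure definition suggests it may be deliberate. The formal Aim does not say preoperative, and the postoperative-care use fits this baseline. The intake description may also define only the source population. None of this reconciles the chosen origin with the two explicit statements that the prediction applies before treatment.

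Finally, calibration in the development sample tests only the quantity modelled, under any design. That is true, and it is why good calibration here cannot support the preoperative claim.

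**Conclusion.** The concern holds and needs correction before the score chart is built. The mismatch is certain from the text, given the inference that an implant without a baseline date cannot be analysed. To the same end date, the displayed risk is too low for preoperative use whenever any early loss occurs. The amount cannot be determined from the documents. It is 0.4–4.8 points under the assumed general ranges, and roughly 1 point (low-risk profile) to 4–8.5 points (high-risk profile) in the survival illustration. The absolute gap is larger for the high-risk profile and the relative gap smaller. These figures are illustrations, not estimates for this cohort.

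**What to change.** Set time zero at the date of implant placement, include every placed implant, and count loss or removal before the suprastructure as failure. Censor implants never restored for other reasons at last contact. Keep the suprastructure-based model as a secondary landmark analysis, which suits the postoperative-care use. State the prediction horizon and the date from which it counts.

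If placement dates or early losses cannot be retrieved, restrict the aim, score chart and claims to risk given that the implant reached suprastructure placement, and delete the two statements that the prediction applies before treatment. Either way, report how many implants were lost before the suprastructure, as far as the records allow.

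The first option costs one more date and the early-loss records, extracted from the same patient record system; the documents do not establish that these are available. The second costs a narrower claim and a change of wording.

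### The Cox models treat implants as independent although one patient may have several, so standard errors for patient-level predictors come out too small; the score chart is not labelled as risk per implant

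*Combined protocol and SAP*

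**What the plan says.** Under Study design, adult patients enter at first intake for one or more implants, and nothing restricts the analysis to one implant per patient. Under Outcomes, both failure and follow-up time belong to the implant. The candidate predictors cover "demographic characteristics, lifestyle habits, general health, dental health, and implant characteristics"; the first three of these domains take a single value for all implants of a patient.

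The Statistical analysis section gives the method: "The univariate and multivariate Cox regression analysis is used to identify important risk factors for the failure of dental implants". For calibration, "the included implants are separately grouped into deciles based on their predicted risk of failure". It mentions no cluster term, robust variance, frailty or random effect.

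The background (What is already known) describes two earlier prediction studies, one using a marginal model for clustered data and the other a frailty model. The plan faults them for few predictors, no score chart and no assessment of performance, but not for how they handled clustering. It adopts neither approach and gives no reason. For a patient with two implants in the second study, it reports that "the probability that 1 implant would survival 12 months was 85.8% and the joint probability of surviving for 12 months was 75.1" per cent, and that if one implant had already survived 12 months, "then the second implant had an 87.5% chance of surviving 12 months".

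On the chart, the Statistical analysis section says it is made "in order to facilitate the calculation of the failure rate of implants". Under What is new, clinicians add up a score for the patient and "find out the corresponding predicted probability of the failure rate of dental implants of each individual patient".

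**The concern.** Implants in one mouth share the patient's biology, habits and care, so their outcomes tend to go together. A Cox model with one record per implant and the usual model-based variance counts each implant as a separate piece of information. For a predictor that is constant within a patient, this overstates the information: confidence intervals are too narrow and p-values too small. Identifying important risk factors is one of the two parts of the stated aim, and the error leans towards declaring too many. If significance also decides which predictors enter the model, the chart inherits the problem; the plan states no selection rule.

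A secondary point is the unit of the chart. A score summed for the patient, with output described as belonging to the individual patient, can be read as that patient's chance of any failure. The model gives a risk per implant, and for a patient with several implants the two differ.

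**Working it through.** **Inputs**

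- From What is already known: 12-month survival of one implant 0.858, joint survival of two 0.751, conditional survival of the second 0.875.
- Implants per patient, *m*: not given. Assumed 2 to 4. The title of reference 6 gives 121 implants in 46 patients, 121/46 = 2.63, which serves as a middle value.
- Failure proportion: 5% (from the 95% five-year survival in the introduction, which counts implant loss only) and 12% (assumed).
- Two-sided 5% level and 300 patients: assumed. The plan gives no alpha, sample size or event count.

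**1. Cited figures.** They agree with each other: 0.858 × 0.875 = 0.751. Independence would give 0.858² = 0.736, so the correlation is positive.

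**2. Implied within-patient correlation.**

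ρ = (0.751 − 0.858²) / (0.858 × 0.142) = 0.0148 / 0.1218 = 0.122

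Rounding of the inputs allows 0.111 to 0.133.

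**3. Effect on a patient-level predictor.** Design effect DE = 1 + (m − 1)ρ; standard error ratio = √DE; actual level of a nominal 5% test = 2[1 − Φ(1.96/√DE)].

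| m | DE | true SE / naive SE | actual level |
|---|---|---|---|
| 2 | 1.12 | 1.06 | 6.4% |
| 2.63 | 1.20 | 1.10 | 7.3% |
| 4 | 1.37 | 1.17 | 9.3% |

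**4. Rarer failure.** The 0.122 applies at 14.2% failure. A shared gamma frailty that reproduces the cited figures has variance θ solving (2 × 0.858^(−θ) − 1)^(−1/θ) = 0.751, which gives θ = 0.98. Under that frailty ρ falls to 0.105 at 12% failure and 0.047 at 5%. At 5% failure the standard error ratios for m = 2, 2.63 and 4 become 1.02, 1.04 and 1.07, and the levels 5.5%, 5.9% and 6.6%.

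**5. Simulation.** Shared gamma frailty θ = 0.98, 300 patients, a 50:50 patient-level predictor with no true effect, 12,000 runs per scenario. Actual level of the naive 5% test:

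| Implants per patient | 12% failure | 5% failure |
|---|---|---|
| exactly 2 | 5.4% | 5.2% |
| mean 2.63 | 7.9% | 5.6% |
| 4 (fixed, or varying with mean 4) | 8.9–9.9% | 6.2–6.5% |
| very uneven (geometric, mean 4) | 12.5% | 8.2% |

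At a mean of 1.5 implants the level was 4.3–5.5%. Tests clustered by patient gave 4.1–5.5% throughout. Predictors varying at random within a patient gave 4.1–5.0% without correction. Repeat simulations of 6,000 runs agreed with the table to within about one percentage point.

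Fitting with R `coxph` (1,500 runs, mean 2.63, 12% failure) gave 7.6% naive and 4.5% clustered, with identical coefficients.

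**6. Chart unit.** In the cited two-implant example, risk per implant is 1 − 0.858 = 14.2%, and the chance that at least one of the two fails is 1 − 0.751 = 24.9%.

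**The case against.** The plan sets no significance level, confidence interval or selection rule, so the harm presumes a test that it does not specify. Candidates are also screened beforehand by literature, guideline and experts, so an error rate under no effect describes only part of the list. The main product (coefficients, scores, C-index, calibration plot, accuracy at the cutoff) consists of point estimates, which clustering the variance leaves alone. The correlation is borrowed from another study's fitted model, for one patient profile at 12 months, whereas this plan starts its clock at the suprastructure and counts peri-implantitis. Implants per patient are unknown, and most patients may have one. Finally, a failure rate of implants reads naturally as a rate per implant.

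Much of this stands as a limit on size. The correlation shrinks as failures become rarer, so the formula figures in step 3 are too high for a 5% failure proportion; the plan's composite failure should, however, be commoner than implant loss alone. The true correlation here could be lower or higher. For a fixed predictor set the chart does not change.

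The objection does not remove the defect. Regression meant to identify risk factors needs some statement of uncertainty, and any such statement from the analysis as written would be too confident for patient-level predictors. Nothing in the plan shows that this cohort lies in the harmless range. The labelling point is the weaker half: it concerns wording, and the main conclusion does not depend on it.

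**Conclusion.** The concern holds. With several implants per patient and positive correlation, the analysis as written understates standard errors for predictors shared by a patient's implants, in the direction of too many declared risk factors. The direction is firm, but the size is not. With the correlation taken from the cited study and an assumed 2 to 4 implants per patient, the simulated level of a nominal 5% test is about 5% to 10%, and up to 12.5% if numbers per patient are very uneven. If most patients have one implant there is little effect. Predictors that vary at random within a patient are not affected. The chart's unit is left open and should be stated. This should be fixed before analysis: the remedy is simple, and the plan's own background points to it.

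**What to change.** In Statistical analysis, state that implants are clustered within patients and that all Cox models use a robust (sandwich) variance with the patient as cluster, for example `coxph` with `cluster(patient)` in R. Base confidence intervals and any significance-based selection of predictors on that variance. Report the number of patients and the distribution of implants per patient, so that readers can judge how much clustering matters.

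In Statistical analysis and in What is new, label the chart's output as predicted failure risk per implant, and say that it is not the chance that at least one of a patient's implants fails.

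The cost is one term in the model code, in software already named, a short descriptive summary and two wording edits. The downside is slightly wider confidence intervals and possibly fewer predictors declared important. If nearly all patients turn out to have one implant, the results will hardly change.

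### Cox coefficients estimated on the study's own data go into the score chart and individual risks with no shrinkage or optimism correction, so predicted risks will tend to be too extreme in new patients

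*Combined protocol and SAP*

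**What the plan says.** Under Predictors, candidates are narrowed before any outcome modelling. A list drawn from the literature and the Dutch guideline comes first, then "the list of the predictors is sent to the international experts from the International Team for Implantology (ITI) for further screening", and finally "the short list of the potential predictors is determined based on the experts' opinions and the availability of the predictors". The number of candidates is not given, only their domains: "The potential predictors include five domains: patients' demographic characteristics, lifestyle habits, general health, dental health, and implant characteristics".

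The section on statistical methods states: "The univariate and multivariate Cox regression analysis is used to identify important risk factors for the failure of dental implants". That sentence, which names model development as the second purpose of the same regressions, is the whole description of model building. It gives no entry rule, threshold or order of steps. The section then assesses calibration, by deciles of predicted risk among the included implants, and the C-index. Next it divides each regression coefficient by the smallest one and rounds to obtain points. A score chart and line chart convert the points to failure risk. Under What is new, the stated use is a predicted probability for each individual patient.

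Nowhere do the documents mention shrinkage, penalisation, bootstrap, cross-validation or external data.

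**The concern.** Coefficients chosen and estimated on one data set are, on average, too far from zero when applied to new patients. The effect is largest with few failures per candidate. For a tool meant to give individual probabilities, this means that high-risk patients are told too high a risk and low-risk patients too low a risk. Nothing in the plan corrects this, and the planned assessment would not reveal it.

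A second, conditional issue concerns the first aim, the list of important risk factors. If univariate significance is the gate into the multivariable model, factors that guideline and experts have already vetted could be discarded because their unadjusted estimate missed a threshold by chance or was masked by another factor.

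**Working it through.** **Inputs.** The documents state no sample size, failure count, selection threshold or coefficient, so there is no figure to reproduce. The cohort is every consenting adult seen "at their first intake for placement of dental implant(s) from September 2009 to September 2013". Implant survival in the cited literature "is around 95% in the 5-year follow-up and around 90% in the 10-year follow-up", but failure here also counts peri-implantitis and mobility. Assumed: 10% failure at 5 years, 20 binary candidates, 500 to 4,000 independent implants (about 50 to 430 failures).

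**1. Why the decile plot is blind to this.** Take the fitted linear predictor and refit it as the only covariate in a Cox model on the same data. Its coefficient is 1, because the maximum partial likelihood solution already satisfies that score equation. Apparent slope is therefore 1 however overfitted the model is. The plot can show a wrong functional form, but not over-extreme coefficients.

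**2. Calibration slope on new data.** Simulated truths: dense (8 of 20 candidates real, hazard ratios 1.3 to 2.0 in size, 120 runs) and sparse (3 of 20 real, hazard ratios 2.0 to 2.5, 60 runs). Validation was on 8,000 fresh implants. Screened means univariate p<0.05, then an unshrunken multivariable fit. Full means all 20 candidates, unshrunken. Risk error is the root mean square error of predicted 5-year risk. Slopes are medians.

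| Truth | Failures | Real predictors lost by screen | Slope: screened | Slope: full | Slope: ridge on all 20 | Risk error: screened | Risk error: ridge |
|---|---|---|---|---|---|---|---|
| Dense | 53 | 61% | 0.64 | 0.46 | 1.03 | 0.059 | 0.051 |
| Dense | 101 | 40% | 0.75 | 0.63 | 0.96 | 0.046 | 0.042 |
| Dense | 205 | 28% | 0.85 | 0.78 | 0.99 | 0.036 | 0.033 |
| Dense | 414 | 22% | 0.89 | 0.87 | 0.97 | 0.030 | 0.023 |
| Sparse | 53 | 12% | 0.75 | 0.50 | 1.00 | 0.051 | 0.055 |
| Sparse | 109 | 1% | 0.86 | 0.70 | 1.00 | 0.036 | 0.044 |
| Sparse | 216 | 0% | 0.90 | 0.81 | 0.98 | 0.027 | 0.033 |
| Sparse | 433 | 0% | 0.94 | 0.91 | 1.00 | 0.019 | 0.024 |

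Every unshrunken model, screened or full, had a slope below 1. Over all screening thresholds tried, the medians ran from 0.58 to 0.96. At about 100 to 200 failures the p<0.05 screen gave 0.75 to 0.90.

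**3. What such a slope means.** Suppose an implant carries two factors, each with an estimated hazard ratio of 2.0, so 4.0 combined, against a reference implant correctly at 10% risk. The chart gives 1 − 0.90^4 = 34%. With slope 0.75 the true ratio is 4^0.75 = 2.83, and the risk is 1 − 0.90^2.83 = 26%. With slope 0.90 the ratio is 4^0.90 = 3.48, and the risk is 31%.

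**4. Shrinking the same procedure.** In a further simulation with 20 candidates and about 100 to 200 failures, the screened unshrunken model had slopes of 0.77 to 0.90. Bootstrap shrinkage of that same procedure brought them to 0.97 to 0.99. Risk error was equal or slightly lower under both dense and sparse truths.

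**5. Chance that a real predictor passes a univariate screen, if there is one.** With d failures and prevalence q, the probability is approximately Φ(√(d·q·(1−q))·ln HR − z). For HR 1.5, q = 0.20, d = 100 and p<0.05, √16 × 0.405 − 1.96 = −0.34, which gives 0.37. At 50, 200 and 400 failures it is 0.21, 0.63 and 0.90. At p<0.20 the four values, from 50 to 400 failures, are 0.45, 0.63, 0.84 and 0.98.

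**6. Effect of the planned score rule.** With a uniform factor s, the points are (s·b_j)/(s·b_min) = b_j/b_min, so s cancels. If weak predictors are kept, b_min approaches zero. In a simulated set of 20 candidates with 8 real and roughly 130 failures, the median ratio of largest to smallest coefficient was about 78 unshrunken and 62 with a fixed ridge penalty, against 1.5 after screening.

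**The case against.** A reader might infer that the plan commits to a univariate significance filter that discards real predictors. The text does not say so. Scoring each included predictor implies some selection, but not by which rule. Univariate results could be purely descriptive.

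A reader might also infer that the resulting risks must be worse than those from one shrunken model holding all candidates. That fails under the sparse truth. There the screened model had lower risk error than ridge at every size (0.036 against 0.044 at about 109 failures) and lost 1% or fewer real predictors from that size upward.

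Nor is sparsity implausible. The earlier clustered analysis cited under What is already known gives 5-year survival of 93.4% and 27.6% for profiles differing in three factors. Under proportional hazards the combined ratio is ln(0.276)/ln(0.934) = 18.9, or about 2.7 per factor, larger than any effect simulated here. It is a different cohort and does not prove sparsity, but it rules out treating weak effects as given.

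Finally, screening is not the main cause of the extreme coefficients, since the unshrunken full model was more extreme than the screened one at every size. Gains in C-index are small (0.632 against 0.624 at about 101 failures, dense truth).

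All of this stands. It limits the point on selection and shifts the weight to missing shrinkage. It does not remove the slope below 1, which appeared under both truths.

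**Conclusion.** The point holds in this form. With no shrinkage or optimism correction, predicted risks will tend to be too extreme in new patients, with a slope of about 0.75 to 0.90 at about 100 to 200 failures, and the planned calibration check will not show it. Loss of real predictors is a possible further consequence if univariate p-values decide entry. Its size ran from none to 61% across the settings tried, so no single figure can be attached to this study.

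The sizes rest on assumed numbers of candidates, implants and failures and on assumed effect sizes. Implants were treated as independent. Clustering within patients would lower the effective number of failures, which would be expected to worsen the slope. The direction of the miscalibration did not depend on which truth was assumed.

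**What to change.** - State the numbers of candidate predictors, patients, implants and failures, and state the selection rule.
- Keep univariate hazard ratios as description only. Fit the expert shortlist in one multivariable Cox model. If a shorter chart is wanted, reduce the model by a rule written down in advance.
- Repeat the whole procedure, including any reduction, in a bootstrap that resamples patients. Report the optimism-corrected C-index and calibration slope.
- Apply the resulting shrinkage factor to the coefficients, or use a penalised fit, and re-estimate the baseline hazard before the score-to-risk line chart is drawn. Because a uniform factor leaves the points unchanged, it has to enter through that conversion.
- If weak predictors are kept, replace the smallest-coefficient divisor with a fixed one.
- Do not use the unshrunken full model as the remedy.

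Cost: plan wording and a little more analysis code in R, which is already named. The data are retrospective, so nothing new has to be collected. The chart may carry more predictors. This is a cheap improvement.
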